Theory-based algorithms to estimate reliability⁶⁷. The ERA toolbox also provides an estimate for the length of a task that is needed to achieve a particular reliability score for all conditions and groups and in this way serves to optimize the length of a task for clinical research. Recent publication guidelines from leading journals require reliability estimates be published and recommend a cutoff of 0.8 for an ERP to be considered reliable.

Short-term Plasticity – Roving Mismatch Negativity (rMMN) (30 min): We will utilize a rMMN paradigm⁶⁹ that can assess STP by systematically manipulating the number of standard stimuli that appear before a deviant. The rMMN presents a series of identical “standard” stimuli for a set number of repetitions (i.e., either 2, 6 or 36

[figure not shown]

Figure 3: Roving MMN paradigm. Standard (S) stimuli change in pitch (height of bar) and become the deviant (D), which then becomes the new standard.

times) followed by a “deviant” stimulus (differs in frequency from the standards). With each change in the standard series, the deviant stimulus changes in pitch (in 50 Hz steps between 700-1200 Hz) relative to the preceding series of standards, resulting in distinct auditory stimuli that serve as both standards and deviants during the run. Subjects will ignore the tones and perform a visual attention task (press a button when fixation cross changes contrast) which serves to direct attention away from the tones. A schematic of the paradigm is shown in Figure 3. Stimuli are presented in 4, 5-minute blocks, with a 60 s break after each block. rMMN will be presented in between post-modulation blocks in the LTP task (see below). Auditory stimuli, presented via earphones, consist of 80 dB tones; the interstimulus interval is 400 ms. There are 85 deviant trials in each block. Data will be processed with established methods⁴⁰: segmented (-100 to +500 ms time-locked to stimulus onset), ocular correction⁸¹, baseline correction, and finally artifact rejection. MMN is scored as the mean amplitude between 100-200 ms over fronto-central electrodes (F1, Fz, F2, FC1, FCz, FC2) for the difference between deviants – standards. Plasticity is defined as the change in slope of MMN amplitudes over the change in the number of standards (i.e., difference in MMN amplitude after the most standards (36) and fewest standards (2)), with a larger slope indicating greater plasticity.

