Feasibility Data: Data from a sample of SCZ patients is presented in **Preliminary Studies**. For TBI, we piloted this task in two individuals to demonstrate valid ERPs can be obtained. Figure 4 shows ERP difference waves after short, medium, and long standard repetitions.

MMN can be observed as a negative voltage between 100-200 ms that increases in size in response to larger number of standard stimulus repetitions. These data demonstrate that people with TBI provide valid data in the expected direction, suggesting that this task can be validly administered in the proposed sample.

[figure not shown]

Figure 4: Roving standard MMN paradigm in two Veterans with TBI. MMN_S, MMN_M, MMN_L refer to difference waves (deviant – standard waves) for short (S), medium (M), and long (L) series of standards.

[figure not shown]

Figure 5: Overview of the Visual Modulation LTP Paradigm. VEPs are assessed in two blocks prior to modulation, and in 3 blocks (5, 15, and 25 minutes) after modulation. VEPs to the large and small checkerboard pattern are assessed. Modulation lasts 10 minutes and utilizes only large checkerboards.

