Long-term Plasticity – Visual Modulation Paradigm: We will assess visual evoked potentials (VEPs) before and after extended exposure (i.e., “visual modulation”) to assess LTP-like plasticity, modeled after⁷⁰ and adapted by our lab. Stimuli consist of two different checkerboard pattern stimuli: one comprised of large black and white checks and the other comprised of small black and white checks. Only the large checkerboard pattern will be used in the modulation block; this will be done to assess input specificity (i.e., plasticity should only be seen to large but not small checkerboards). On alternating trials within a block, the checkerboard pattern reverses color (i.e., black becomes white and white becomes black). The checkerboard stimuli include a small red central dot to facilitate gaze fixation. The task includes 2 baseline blocks, 1 10-minute modulation block, and 3 post-modulation blocks occurring 5, 15, and 25 min after the modulation block (Figure 5). Prior to modulation, the large and small checkerboard stimuli are presented in separate (counterbalanced) blocks, for a total of 80 stimuli for each type of stimulus. For the modulation block, only the large checkerboard is presented for a total of 10 minutes (i.e., 1200 reversals). A total of 40 large and 40 small checkerboard stimuli are presented in separate blocks in each of the three post-modulation blocks. All stimuli are presented at 2 Hz.

We will utilize a data-driven approach to identify time windows and electrodes that show significant differences post-pre modulation^{32, 61}, focusing on time regions and electrodes overlapping with the early sensory VEPs C1, P1, and N1 that occur between 50-250 ms. Once these are identified, a PCA^{63, 71} applied to the original waveforms will be used to isolate ERP components (e.g., C1, P1, N1) falling within time windows showing significant effects. Amplitudes will be calculated for each identified component and used in analyses. This method provides an objective, unbiased method of selecting components that show task-related modulation.

Feasibility Data: Data from a sample of SCZ using a similar paradigm is presented in **Preliminary Studies**. For TBI, we piloted the new task in 2 individuals to demonstrate that valid waveforms can be obtained. Figure 6

[figure not shown]

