Figure 6: Visual modulation LTP paradigm data in two Veterans with TBI. The P1 (~120 ms) is higher at all three time points in comparison to pre-modulation (baseline) for tetanized stimuli.

shows VEPs recorded before modulation (“baseline”) and 5, 15, and 25 minutes after modulation (Post 1, 2 and 3, respectively). The P1 VEP (positive voltage at ~120 ms) increases in amplitude after 10-minute modulation using modulated stimuli (i.e., large checkerboards; top of figure) but not to non-modulated stimuli (bottom of figure). These data demonstrate that people with TBI can perform the task and provide valid data, lending confidence that this task can be successfully used in the proposed sample.

D6. Cognitive Assessments:

Non-social cognition: MATRICS Consensus Cognitive Battery (MCCB)^{72, 73}: The MCCB assesses 6 domains of cognitive functioning: speed of processing, attention/vigilance, working memory, verbal learning, visual learning, and reasoning/problem solving. Raw values are converted to *t*-scores adjusted for age and gender. An overall composite score is calculated. Time: 60 min.

Social cognition: Empathic Accuracy (EA) task⁷⁴: The EA task consists of 13 video clips lasting 2.0-2.5 minutes of an individual (“target”) discussing a positive or negative experience. After speaking of their experience, the targets provided a continuous rating of how they were feeling. Participants view each video clip and continuously rate how they think the target is feeling. The primary dependent variable is the average correlation between the participant’s and target’s ratings. Time: 30 min.

Social cognition: Facial Emotion Recognition (FER) task⁷⁵: The FER consists of faces of Caucasian and Asian actors portraying one of 6 emotions (afraid, angry, disgust, happy, sad, surprise) or neutral, drawn from a facial expression stimulus data library⁷⁶. The participant selects the expression they think is correct. Eight trials per expression are shown. The primary dependent variable is the total number correct. Time: 15 min.

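### Can four 5-minute rMMN blocks be run around VEP blocks set at 5, 15 and 25 minutes after modulation?

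*Combined protocol and SAP*

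**What the plan says.** Everything relevant is in section D5 of the combined protocol and SAP.

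- The roving MMN paragraph is headed "Roving Mismatch Negativity (rMMN) (30 min" and describes the layout as "Stimuli are presented in 4, 5-minute blocks, with a 60 s break after each block". It gives 85 deviants per block.
- The same paragraph places the task: "rMMN will be presented in between post-modulation blocks in the LTP task (see below".
- The visual modulation paragraph has "3 post-modulation blocks occurring 5, 15, and 25 min after the modulation block". The Figure 5 caption repeats the times: "VEPs are assessed in two blocks prior to modulation, and in 3 blocks (5, 15, and 25 minutes) after modulation". So does the feasibility paragraph, which ends its list of times with "25 minutes after modulation (Post 1, 2 and 3, respectively".
- The content of each VEP block is given as "A total of 40 large and 40 small checkerboard stimuli are presented in separate blocks in each of the three post-modulation blocks", and the rate as "All stimuli are presented at 2 Hz".

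The text does not say which interval holds which tone block, whether any tone block comes before the first or after the last VEP block, or whether the VEP times mark the start of a block. The drawing in Figure 5 was not available for this check. Its caption does not mention the tone task.

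**The concern.** Three VEP blocks have only two gaps between them, and the VEP times are fixed and stated three times. If the placement sentence is taken at its word, four tone blocks have to go into those two gaps, and they are too long. Something would then have to give: the number of tone blocks, the breaks, or the VEP times.

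The worry is that sites of measurement labelled 5, 15 and 25 minutes would really fall later, or that tone blocks would be dropped and the MMN slope would rest on fewer deviants. Timing matters more than usual here because the study exists to try out these paradigms and pass their parameters to a larger grant (D8, D9). A reader who wanted to reproduce the session could not do so from this text alone.

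**Working it through.** **Inputs, all from D5.** Four tone blocks of 300 s; a 60 s break after each; VEP blocks at 300, 900 and 1500 s after modulation; 80 checkerboards per VEP block (half large, half small) at 2 Hz; 85 deviants per tone block.

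**Check on the rate.** The modulation block lasts 10 min: 10 × 60 s × 2 Hz = 1200 reversals, which is the plan's own figure. So 2 Hz can be used to derive the length of a VEP block.

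**Literal reading: all tone blocks between VEP blocks.**

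- VEP block: 80 / 2 = 40 s.
- One gap: 600 − 40 = 560 s (9:20). Two gaps: 1120 s (18:40).
- Tones needed: 4 × 300 = 1200 s without breaks; 4 × 360 = 1440 s with them.
- Shortfall: 1200 − 1120 = 80 s, or 1440 − 1120 = 320 s.
- Two tone blocks in one gap need 600, 660 or 720 s (no, one or two breaks) against 560 s. Each gap therefore holds one block, and two of the four fit.

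**Interleaved reading: one tone block before, between and after the VEP blocks.** Take the VEP times as block starts.

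| Start | End | Event |
|---|---|---|
| 0:00 | 5:00 | rMMN 1 |
| 5:00 | 5:40 | VEP (Post 1) |
| 6:00 | 11:00 | rMMN 2, then break to 12:00 |
| 15:00 | 15:40 | VEP (Post 2) |
| 15:40 | 20:40 | rMMN 3, then break to 21:40 |
| 25:00 | 25:40 | VEP (Post 3) |
| 25:40 | 30:40 | rMMN 4 |

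All four blocks fit, and the sequence ends at 30:40, close to the 30 min in the paragraph heading. Deviants kept: 4 × 85 = 340 of 340.

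**What is left.** The only tight place is the first slot.

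- If the break is a pause in the tone task, the 40 s VEP block fits inside the first 60 s break (5:00 to 6:00, as in the table). Nothing conflicts.
- If the break must be idle time, tone block plus break needs 360 s before a VEP block due at 300 s: 60 s short. Either one break is dropped or Post 1 starts at 6:00. Post 2 and Post 3 do not move.
- If 5 minutes marks the middle or the end of the VEP block, the slot is 280 or 260 s. The tone block alone overruns by 20 or 40 s; with an idle break it overruns by 80 or 100 s.

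**What the analysis uses.** D9 is mainly descriptive: completion, tolerability and data quality, reliability, distributions, and exploratory correlations. It contains no model of LTP decay over minutes. The background (A3) describes the effect as lasting up to an hour, so a shift of 20 to 100 s in one of three time points is small on that scale.

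**The case for a change.** The strongest case for a change is that the literal conflict is real and rests only on the plan's own figures. The VEP times appear three times, so they are not a slip, and moving them from block start to midpoint leaves the 10-minute spacing as it is. Any changeover between large and small checks only shortens the gaps. The interleaved layout is nowhere written down, and two of its four tone blocks lie outside the gaps between VEP blocks. A study meant to hand on task parameters should say how the tasks are arranged.

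That much stands: the placement sentence is loose and the order is not stated. What does not stand is that the session cannot be run. One natural layout runs it with every stated duration kept. Nor are all three VEP times at risk, since only the first is tight. The pilot data from two Veterans are no evidence of mistimed blocks either, because nothing says that the tone task was interleaved there. Moving the VEP times to hold two tone blocks per gap would gain nothing: with all breaks, they would become 5:00, 5:40 + 12:00 = 17:40, and 18:20 + 12:00 = 30:20, away from the times the paradigm was piloted with.

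One caveat concerns the tone block itself. If trains of 2, 6 and 36 were equally frequent (an assumption; the mix is not stated), 85 trains would average 44/3 tones, or about 1247 tones and 8.3 min at 400 ms from onset to onset. The first slot would then be too short. A 5-minute block holds 300 / 0.4 = 750 tones, a mean of 8.8 per train, which an unequal mix can give. That is a question about the train mix, separate from where the blocks are placed.

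**Conclusion.** No change to the plan is needed. The literal reading fails by 1:20 without breaks and by 5:20 with them, but it is not the only reading. With the tasks interleaved, all four tone blocks and all 340 deviants fit by 30:40. The most that remains with VEP times as block starts is one 60 s break before Post 1; it disappears if the VEP block runs during that break.

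This rests on three assumptions: tone blocks last the stated 5 minutes, VEP times mark block starts, and switching between tasks takes negligible time. If the VEP times mark the middle or end of a block, Post 1 shifts by 20 to 100 s, depending also on the break, and nothing else moves.

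The gap is one of session detail. Stimuli are run from presentation software (D5), so a block order has to be scripted before the first participant, and a scripted order would be the same for everyone. Actual VEP times can be read from the recorded stimulus onsets. No deviants need be lost, no planned analysis uses minute-level timing, and no conclusion under any of the three aims would change.

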Veterans with TBI, given the similar disturbances in cognition and functional outcome. In this section we discuss our EEG studies of neuroplasticity in Veterans with SCZ. The goals of this SPiRE are to examine neuroplasticity in SCZ and TBI using novel EEG methods, to provide an objective biomarker to assess neuroplasticity, and to understand how determinants of outcome (e.g., cognition) are related to neuroplasticity.

Roving mismatch negativity (rMMN): We recently published a study examining the relationship between MMN and auditory hallucinations in SCZ⁴⁰. This study utilized one version of the roving MMN paradigm that is proposed in the current application (see **D5** below). In our study, we found that the ERP response to the deviant increased in amplitude as the number of standards presented increased, reflecting STP. However, this increase in STP was significantly smaller in SCZ than in healthy controls (Figure 1).

Long-Term Potentiation (LTP): Our lab recently published on EEG-based measures of LTP *in vivo* in Veterans with SCZ and healthy controls³⁰; this was only the third such study published in this population. As discussed in **Section A**, LTP is assessed in this paradigm by comparing visual evoked potentials before and after HFS. We performed t-tests on post- minus pre-HFS difference waves and subjected them to data-driven mass univariate analyses (correcting for the vast number of comparisons) to identify time windows and electrodes with clear signals (Figure 2).

The difference waves are plotted as topographical maps; in the raster plot, significant post-pre HFS differences at each time sample and electrode are shown in blue, demonstrating significant LTP between 140-227 ms over parieto-occipital electrodes 2 minutes after HFS. We utilized the same paradigm in the only other paper examining SCZ-control differences in LTP³². However, more recent paradigms have been developed with improved features, such as the ability to evaluate input specificity and longer time frames for LTP assessment, so we will use a newer approach in the current study (see **D5**).

D. Research Design and Methods

D1. Study Overview:

This is a 2-year study to assess EEG-based

[figure not shown]

Figure 2: Visual HFS LTP Paradigm. Topographical map of the post-pre difference wave (Panel A) and raster diagram (Panel B) illustrating significant differences. Significant LTP was found (in blue) between 140 and 227 ms for the 2 minute post-HFS block

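### LTP components are kept only where the post-pre change is significant, with no fallback, so the Aim 2 LTP mean can be overstated or missing

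*Combined protocol and SAP*

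**What the plan says.** Section D5 (Long-term Plasticity – Visual Modulation Paradigm) sets three steps.

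1. Screen: "We will utilize a data-driven approach to identify time windows and electrodes that show significant differences post-pre modulation". The search is directed to 50–250 ms, around the early visual components C1, P1 and N1.
2. Run a PCA on the original waveforms and isolate the components "falling within time windows showing significant effects".
3. "Amplitudes will be calculated for each identified component and used in analyses".

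The section concludes: "This method provides an objective, unbiased method of selecting components that show task-related modulation".

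D9 (Aim 2) then describes the distribution, mean and SD of the neuroplasticity measures in each group. Exploratory Aim 3 correlates those measures with cognition, functioning and each other. The sample is 25 per group, 75 in all (D2).

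The documents do not state:
- an alpha or multiplicity correction for this screen;
- whether it is run on the pooled sample or by group;
- a separate selection sample or a default component;
- what happens if no window is significant.

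Section C describes an earlier study with a different stimulation paradigm, which used "data-driven mass univariate analyses (correcting for the vast number of comparisons") and is reported as "demonstrating significant LTP between 140-227 ms over parieto-occipital electrodes 2 minutes after HFS". For two pilot participants with TBI, D5 reports: "The P1 VEP (positive voltage at ~120 ms) increases in amplitude after 10-minute modulation using modulated stimuli". Neither result is named as a default. For roving MMN, by contrast, D5 fixes a 100–200 ms window and six electrodes in advance.

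**The concern.** The LTP effect is the post-pre change. A component is retained because that change was significant in this sample, and its mean change is then reported from the same sample. Studies in which noise pushed the change upward pass more often, so the mean, given that it is reported, sits above the true value.

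Running the PCA on the original waveforms weakens the link between the screened value and the score. It does not break it, because retention still depends on the post-pre test.

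The second risk is absence. If nothing passes, the plan as written yields no LTP score for Aim 2 and leaves the Aim 3 LTP correlations undefined. It is also open which component the Aim 1 LTP reliability and trial-count results describe. The Aim 1 completion, tolerability and data-quality targets are untouched.

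This matters because Aim 2 exists to supply these estimates for later studies.

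**Working it through.** **Inputs.** From the documents: n = 25 per group and 75 pooled (D2); search region 50–250 ms and 512 Hz sampling (D5). The plan gives no figure for LTP size, so there is none to reproduce. Assumed: true change d = 0.2, 0.3 or 0.5 SD of the individual post-pre change; two-sided alpha 0.05; noise correlation ρ between screened window and reported score of 0.4 to 1.0.

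**Model.** For each participant, window = d + z and score = d + ρz + √(1−ρ²)·e, with z and e independent standard normal. The score is reported only if the one-sample t of the window is significant (200,000 simulated studies per case).

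**Hand check (pooled, d = 0.3, ρ = 1, normal approximation).** SE = 1/√75 = 0.115; expected t = 0.3 × √75 = 2.60; critical value 1.99.
- P(kept) ≈ Φ(2.60 − 1.99) = Φ(0.61) = 0.73.
- Mean if kept ≈ 0.30 + 0.115 × φ(0.61)/Φ(0.61) = 0.30 + 0.115 × 0.331/0.729 = 0.352.
- Ratio 0.352/0.30 = 1.17, as simulated.

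The excess scales with ρ: 0.17 × 0.4 = 0.07, which gives the lower end of 1.07.

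**Reported mean ÷ true mean, and share of studies in which the component is kept (two-sided 0.05).**

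| True change | Pooled, n = 75 | Kept | By group, n = 25 | Kept |
|---|---|---|---|---|
| 0.2 SD | 1.22–1.55 | 40% | 1.56–2.41 | 16% |
| 0.3 SD | 1.07–1.17 | 73% | 1.29–1.74 | 30% |
| 0.5 SD | 1.00–1.01 | 99% | 1.08–1.21 | 67% |

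At 0.8 SD with ρ = 1 the ratio is 1.00 pooled and 1.02 by group. The SD is 0–2% low pooled and 1–7% low by group.

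**No component kept.** Three components with correlation 0.3 (60,000 studies). The range runs from all three changing at p < 0.05 to only one changing at p < 0.05/3.

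| True change | Pooled | By group |
|---|---|---|
| 0.3 SD | 5–42% | 41–81% |
| 0.5 SD | 0–3% | 8–51% |

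The upper ends at 0.3 SD can be checked by treating the components as independent. The changing component is missed with probability 0.439 (pooled) or 0.837 (by group), and each null component with probability 0.983. So 0.439 × 0.983² = 0.42 and 0.837 × 0.983² = 0.81.

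**Group differences and correlations.** Pooled screen, true means 0.45/0.30/0.15, true r = 0.30 (40,000 studies). Kept means are 0.47/0.32/0.17 at ρ = 0.4 and 0.50/0.35/0.20 at ρ = 1.0. The difference between the outer groups is 0.29–0.30 in kept studies against 0.30 in all studies. The within-group correlation is 0.29 against 0.29–0.30.

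**If the screen is corrected for multiplicity**, as in the earlier study. Six electrodes with noise correlation 0.7, noise smoothness FWHM 25 or 50 ms, max-t threshold at 5% familywise (3.4–3.7 at n = 75, 3.8–4.2 at n = 25), P1 kept if any sample in 100–145 ms passes, 1,500 studies per case. The ratio is for P1.

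| True change | Pooled: ratio; no score | By group: ratio; no score |
|---|---|---|
| 0.2 SD | 1.7–1.8; 46–87% | 2.3–2.7; 87–94% |
| 0.3 SD | 1.2–1.4; 5–64% | about 2.0; 72–91% |
| 0.5 SD | 1.01–1.04; 0–12% | 1.3–1.4; 20–73% |

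Correction controls false findings. It increases both the overstatement and the chance of no score.

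**The case against.** **The bias is small beside the sampling error.** A group mean on 25 people has SE 1/√25 = 0.20 SD. With an uncorrected pooled screen at d = 0.3 the excess is 0.02 to 0.05 SD, a quarter of one SE or less. D9 presents the analyses as mainly descriptive, and the SD and correlations hardly move. This stands and limits the finding's weight, although at d = 0.2 the excess reaches 0.2 × 0.55 = 0.11 SD and a corrected screen makes it larger.

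**The largest figures need a screen in each group.** D5 does not describe one, and a single pooled screen is at least as natural a reading. That is fair, but the plan does not settle it.

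**Every effect-side input is assumed, and no PCA was simulated.** True. The upper ends of the uncorrected ranges (ρ = 1) describe a score identical to the screened value. In the corrected-screen simulation, the score correlated 0.81 to 0.92 with the largest t in the window.

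**Earlier evidence makes a null screen unlikely, and nothing bars scoring C1, P1 and N1 after one.** The earlier effect lay at 140–227 ms under a different paradigm, and the pilot effect at about 120 ms in two people. They make a null less likely but do not settle which component would be kept. A component scored after a null screen would be a post hoc choice that the plan does not provide for.

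**The claim of lack of bias concerns selection, not estimation.** That is a reasonable reading, but readers of an Aim 2 mean may not draw the distinction.

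**Conclusion.** The concern holds. As written, the plan reports the LTP mean only after a significant post-pre screen in the same participants, and gives no rule for a null screen.

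The size depends on the unknown true change and on unstated choices. With a pooled screen it is negligible at 0.5 SD (at most about 4%, even if corrected). At 0.3 SD pooled it is 7 to 17% uncorrected, or about 20 to 40% corrected. It is substantial for a screen within each group at 0.3 SD or below. The risk of having no score is real at 0.3 SD under either rule.

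The harm is confined to the LTP mean and to the availability of the measure for Aims 2 and 3 and for Aim 1 reliability. The plan should be changed because the remedy is cheap. Confidence in the size is medium.

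**What to change.** Define C1, P1 and N1 windows and electrodes without using the post-pre contrast. The simplest way is to fix them in advance within 50–250 ms, as D5 already does for roving MMN. Report mean and SD by group for all three, whatever their significance. Keep the mass-univariate map as a descriptive display, and state its alpha, its correction and whether it is pooled. Limit the claim of lack of bias to freedom from investigator choice.

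An alternative is to locate components on a PCA or grand average collapsed over pre/post, check size and all participants. This is neutral only if the collapsed average is uncorrelated with post-pre noise, which requires w_post × var_post = w_pre × var_pre. The baseline has "for a total of 80 stimuli for each type of stimulus" and the three post blocks give 3 × 40 = 120.
- **Trial noise only:** weights 80/200 = 0.4 pre and 120/200 = 0.6 post satisfy the condition. In a null check taking the largest of 20 points, they gave a false change of 0.00 SE, against −0.37 SE for equal weights.
- **Added equal pre/post occasion variance of 0.1 (trial variance 1):** trial weights gave +0.34 SE and equal weights −0.03 SE.

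Since the variance structure is unknown, fixed windows are safer.

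The cost is analysis-plan wording, with no new data. LTP means may look smaller, three components are reported instead of only those that pass, and an effect off the component peaks or outside a fixed window would appear only in the descriptive map.
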